Patients will be asked to rate their stool consistency according to the BSFS (see **Appendix C**), which will be provided to them in the form of a laminated card (and will appear on the appropriate electronic hand-held device screen) at the Screening Visit (Visit 1), and may be referred to as often as necessary throughout the Screening, Treatment and Posttreatment Periods. The BSFS is a validated measure of stool consistency commonly used in clinical trials.

Use of Rescue Medication (RM)

As part of the daily diary, the patient will be questioned concerning the use of provided rescue medication (Dulcolax®), including time of use, frequency of use, and amount of rescue medication used. Use of rescue medication will determine whether a BM was spontaneous, but only this aspect of rescue medication use is part of the primary endpoint.

Constipation-related Symptoms

The patient will also record in the electronic diary the frequency and severity of several CIC-related gastrointestinal symptoms. These symptoms include abdominal pain, abdominal bloating, abdominal discomfort, straining during bowel movement and pain with defecation. Patients will be asked to rate their symptoms on an 11-point Numeric Rating Scale from 0 (NO) to 10 (WORST POSSIBLE) (See **Appendix D**).

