8.8.3 Additional Efficacy Endpoints

Additional efficacy endpoints related to CIC symptoms are:

- Change from baseline in abdominal pain, by study week
- Change from baseline in abdominal bloating, by study week
- Change from baseline in abdominal discomfort, by study week
- Change from baseline in straining during a BM, by study week
- Change from baseline in pain with defecation, by study week

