- Enter the time of the bowel movement in 12 hour format, entering 2 digits for the hours and 2 digits for the minutes.
- For AM press 1. For PM press 2.
- Did you feel like you completely emptied your bowels during this bowel movement? If yes, press 1, if no press 0.

Please refer to the Bristol Stool Scale diagram provided by your doctor's office. Please rate the form/consistency of this stool. For Type 1, press 1, For Type 2, press 2, For Type 3, press 3, For Type 4, press 4. For Type 5, press 5. For Type 6, press 6. For Type 7, press 7.

Rescue Medication usage

- Have you taken any Dulcolax® today? If yes, press 1, if no press 0.
- How many times have you taken Dulcolax® today?
- Enter the time you took Dulcolax® in 12 hour format, entering 2 digits for the hours and 2 digits for the minutes.
- For AM press 1. For PM press 2.
- Enter the number of tablets you took

Daily Symptom Diary

The patient will be asked to rate their symptoms on a scale of 0 to 10, where 0 is NO 'ABDOMINAL PAIN' and 10 is 'ABDOMINAL PAIN' AS BAD AS YOU CAN IMAGINE.

1. Abdominal Pain. Rate your abdominal pain at its worst on a scale of 0 to 10, where 0 is NO PAIN and 10 is PAIN AS BAD AS YOU CAN IMAGINE.
2. Abdominal Bloating. Rate your abdominal bloating at its worst on a scale of 0 to 10, where 0 is NO ABDOMINAL BLOATING and 10 is ABDOMINAL BLOATING AS BAD AS YOU CAN IMAGINE.
3. Abdominal Discomfort. Rate your abdominal discomfort at its worst on a scale of 0 to 10, where 0 is NO ABDOMINAL DISCOMFORT and 10 is ABDOMINAL PAIN AS BAD AS YOU CAN IMAGINE.
4. If you had one or more bowel movement today, rate your straining with a bowel movement at its worst on a scale of 0 to 10, where 0 is NO STRAINING WITH A BOWEL MOVEMENT and 10 is STRAIN WITH A BOWEL MOVEMENT AS BAD AS YOU CAN IMAGINE.
5. If you had one or more bowel movement today, rate your pain with defecation at its worst on a scale of 0 to 10, where 0 is NO PAIN WITH DEFECATION / WITH A BOWEL MOVEMENT and 10 is PAIN WITH DEFECATION / WITH A BOWEL MOVEMENT AS BAD AS YOU CAN IMAGINE

E. PATIENT QUESTIONNAIRES

Patient Assessment of Constipation -Quality of Life (PAC-QOL), Patient Assessment of Constipation -Symptoms (PAC-SYM), Patient Global Assessment (PGA) Questionnaires

PGA will be administered electronically via IWRS, while PAC-QOL and PAC-SYM are paper-based.

PAC-QOL © PATIENT ASSESSMENT OF CONSTIPATION						

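### As printed, the diary's abdominal discomfort item is anchored at the top by abdominal pain, so high discomfort scores would not be cleanly distinguished from pain

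*Combined protocol and SAP*

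**What the plan says.** Section 4.2.1 lists what is rated in the electronic diary: "These symptoms include abdominal pain, abdominal bloating, abdominal discomfort, straining during bowel movement and pain with defecation". It gives one scale for the list and points to Appendix D for the wording: "Patients will be asked to rate their symptoms on an 11-point Numeric Rating Scale from 0 (NO) to 10 (WORST POSSIBLE".

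Appendix D, item 3, instructs the patient: "Rate your abdominal discomfort at its worst on a scale of 0 to 10". The anchors that follow are "0 is NO ABDOMINAL DISCOMFORT and 10 is ABDOMINAL PAIN AS BAD AS YOU CAN IMAGINE".

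The sentence that introduces all five items reads "where 0 is NO 'ABDOMINAL PAIN' and 10 is 'ABDOMINAL PAIN' AS BAD AS YOU CAN IMAGINE".

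Appendix D also notes that the final diary text will be in the Design Specifications for the diary system and in the Study Procedure Manual.

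Section 8.8.3 lists "Change from baseline in abdominal discomfort, by study week" as an endpoint separate from abdominal pain, and section 8.8.3.1 analyses each symptom score on its own. Section 7.1 gives these diary symptoms a second role as safety variables. Sections 4.3.1 and 7.1 say that they should generally not be entered as adverse events as well.

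**The concern.** The stem and the lower anchor of item 3 are about discomfort; the upper anchor is about pain. A patient with very bad discomfort and little pain has no clear answer near the top of the scale. One patient may score the discomfort as asked, while another may hold back because the top is reserved for the worst pain.

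The plan treats the two symptoms as distinct and reports each against placebo. A change in a discomfort score whose upper end is defined by pain cannot be read purely as a change in discomfort. The safety use raises the same difficulty, because there will usually be no parallel adverse event entry to consult. Ratings collected on a mixed scale cannot be converted afterwards to the intended one.

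**Working it through.** The plan gives no figure to reproduce here, and no power or effect-size calculation applies. The check is a comparison of wording, followed by a count of what the item feeds.

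**1. Anchors of the five items in Appendix D**

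| Item | Symptom rated | Lower anchor names | Upper anchor names |
|---|---|---|---|
| Lead-in | all symptoms | abdominal pain | abdominal pain |
| 1 | abdominal pain | pain | pain |
| 2 | abdominal bloating | bloating | bloating |
| 3 | abdominal discomfort | discomfort | **abdominal pain** |
| 4 | straining | straining | straining |
| 5 | pain with defecation | pain with defecation | pain with defecation |

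Item 1 has "0 is NO PAIN and 10 is PAIN AS BAD AS YOU CAN IMAGINE" and item 2 has "0 is NO ABDOMINAL BLOATING and 10 is ABDOMINAL BLOATING AS BAD AS YOU CAN IMAGINE". Item 3 is the only numbered item whose two ends name different symptoms. The lead-in puts its symptom name in inner quotation marks, like a placeholder. Together these suggest a copying error rather than a decision to use a mixed scale.

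**2. Appendix D against section 4.2.1.** The body text runs from absence of the symptom to its worst possible level, and discomfort is on its list. Items 1, 2, 4 and 5 fit that description. Item 3 fits at 0 and not at 10. The lead-in fits only item 1.

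**3. What the item feeds**

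- Ratings kept: section 4.2.1 says that entries before the two-week baseline serve the compliance check only and are not saved. Retained weeks are 2 baseline + 8 treatment + 2 follow-up = 12, or 12 × 7 = 84 evening ratings per patient with a complete diary. With about 120 patients, that is at most 120 × 84 = 10,080 ratings.
- Comparisons: section 8.8.3.1 presents each of three doses against placebo for each of 10 weeks, so 3 × 10 = 30 differences for discomfort. Five symptoms give 5 × 30 = 150, so the affected share is 30/150 = 20%.
- Not fed by this item: the primary endpoint and its analysis (SBMs) and the key secondary endpoints (stool consistency, SBM and CSBM frequency).

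**4. Direction of any effect.** Section 8.4.3 derives the baseline symptom scores from the same diary. If one script is used throughout, the wording is the same in all four arms and at baseline. It does not itself create a difference between arms; it changes what a difference means.

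**5. Size of the effect on the score.** This would need the pain–discomfort correlation and the distribution of the ratings. The documents give neither, so no size is stated.

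**The case against.** The strongest reply is that the printed text is not the instrument. Appendix D defers to two documents that are not available here, and section 4.2.1 already states the intended scale, so the slip may have been caught in the build. This stands as a limit: it is not shown that any patient saw this wording. It does not make the printed text right, because Appendix D is the only item-level wording in the protocol and the one that section 4.2.1 cites.

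Four stronger readings are tempting, and the documents do not support them:

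- **That discomfort cannot be separated from pain.** The stem and lower anchor name discomfort, pain has its own item, endpoint and model, and PAC-SYM rates abdominal discomfort and abdominal pain as separate questions. The blurring is at the upper end. PAC-SYM cannot stand in for the weekly endpoint, however: it is a 0 to 4 rating with two-week recall, given at visits.
- **That scores are compressed and the comparison weakened.** This is plausible, but nothing in the documents shows that compression occurs or how large it would be.
- **That the comparison with placebo is biased.** Identical wording across arms and at baseline does not produce that by itself.
- **That 14 weeks of data are affected.** That is the planned participation, including diary practice that is not saved; retained data cover about 12 weeks.

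It is also fair to say that the stakes are low. Discomfort is an additional endpoint in a trial that calls itself exploratory, and it is not listed consistently: section 2.4.1.3 omits it, while the synopsis and section 8.8.3 include it.

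**Conclusion.** The point holds as an inconsistency in the printed instrument. Item 3 has mismatched anchors, the lead-in names one symptom for all five, and both disagree with section 4.2.1. If deployed as printed, high discomfort scores would not be cleanly distinguished from pain, which weakens the interpretation of one additional efficacy endpoint and of the same score as safety data.

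The importance is minor. The conclusion about interpretation assumes that the final script kept the Appendix D wording, which the documents do not establish. The conclusion that the placebo comparison is not biased by the wording assumes that one script was used throughout, in all arms and from baseline onwards.

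**What to change.** 1. In Appendix D, item 3, replace pain with discomfort in the upper anchor and leave the rest of the phrase unchanged, so that both ends name the symptom being rated.
2. Reword the lead-in so that it refers to the symptom in question rather than to abdominal pain.
3. Before activation, check the final script in the Design Specifications and the Study Procedure Manual against the corrected appendix and section 4.2.1.
4. If the diary is already live with the printed wording, state this as a limitation wherever the discomfort results are reported, for efficacy and for safety.

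Before launch, the cost is one word in item 3, one edited sentence and a check of the script. The sample size and the analysis model do not change. The omission of discomfort from section 2.4.1.3 can be corrected in the same edit.
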